4.4 Study duration and duration of participant's participation

HCWs will be regularly approached for data collection. First, the data collection phase starts with the observations and is then followed by the Ranas questionnaire and the hand-rinse samples (Figure 3). For practical reasons, the hand-rinse samples can be taken right after the questionnaire.

[figure not shown]

Figure 4: Flow-chart of data collection activities at baseline, follow-up and endline of the project depicting observations, the Ranas questionnaire and the hand-rinse samples.

The observations will take approximately 30 minutes to one hour per HCW depending on how many patients visit and hence how many handwashing opportunities arise. The questionnaire will take a maximum of 40 minutes and the hand-rinse samples about 10 minutes. This means that for the Ranas questionnaire and the hand-rinse samples together with the informed consent, the participant will be asked for about an hour of his/her time.

Entering the pre-defined health outcomes in the diary over the course of the year will not take much time of the HCWs. To write down an event will take the HCW about two minutes per event.

Finally, the HCWs of the 12 intervention facilities will be asked to take part in FGDs or interviews. This should not take them longer than one hour. KIIs with stakeholders outside of the health care facilities will also be limited to one hour.

H4H
Version 1 17.01.2023
4.4.1 Schedule of events

	2023												2024															
	Oct	Nov	Dec	Jan	Feb	Mar	Apr	May	Jun	Jul	Aug	Sep	Oct	Nov	Dec	Jan	Feb	Mar	Apr	May	Jun	Jul	Aug	Sep	Oct	Nov	Dec	
h4h project																												
Ethical clearance process (incl. study protocol)	■	■																										
Piloting phase		■	■																									
Data collection				■	■	■	■	■	■	■	■	■	■	■	■	■	■	■										
Intervention phase					■	■	■	■	■	■	■	■	■	■	■	■	■	■				■	■					
Feedback to the community																		■	■							■	■	
Scientific publications											■				■							■						
Data collection																												
Recruitment			■	■																								
Ranas survey				■					■									■										
Handwashing observations				■					■									■										
Hand-rinse samples				■					■									■										
Diary data					■	■	■	■	■	■	■	■	■	■	■	■	■											
FGDs and interviews											■																	
Gravit'eau monitoring data					■	■	■	■	■	■	■	■	■	■	■	■												
Intervention activities																												
Gravit'eau installation					■																		■	■				
Ranas behaviour change					■	■																	■	■				
Chlorination					■																		■	■				
Management of WASH infrastructure					■																		■	■				

4.5 Amendments

All of the different modules will be piloted in pilot facilities of the study regions and adapted to local needs and circumstances.

Substantial changes to the project set-up; the protocol and relevant project documents will be submitted to all of the Ethics Committees for approval according to the local and Northern EC guidelines.

4.6 Withdrawal and discontinuation

Participants may stop their participation at any time and withdraw their consent. Local staff is recruited and employed by Tdh and has to follow the terms and conditions of the local Tdh offices which are written in their work contract.

The overall h4h project or specific project sites can be discontinued due to several reasons by the project leader, such as:

- Ethical concerns (e.g. non-acceptance of proposed technical solutions)
- Insufficient participant recruitment
- Natural hazards (e.g. heavy floods, earthquakes)
- Damage and vandalism of infrastructure, technical failure of interventions
- Alternative interventions and projects at the same facilities not coordinated with us
- Limited access by Tdh staff due to any reason out of their control including pandemics, natural hazards or deterioration of security situation
- Political constraints restricting access to the health care facilities or the project implementation

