
2.3.1 Gravit'eau handwashing station

Gravit'eau is a handwashing station which recycles water with gravity (25). The station does not need to be connected to an electricity source as it is activated by a foot pump. The design of the station is adaptable to the context of use and can hold up to 90 litres of water. The used water is collected and is treated using gravity in a grease trap and by the gravity-driven membrane filtration. The membrane module contains ultrafiltration membrane that removes pathogenic microorganisms. In health care facilities, chlorine can be added as a second barrier. The then pathogen-free water is stored in a storage tank until its next use (<http://www.graviteau.ch>). To keep an acceptable water quality also in terms of color, the water needs to be replaced about once a month and the filter needs to be replaced every five to eight years (25).

In contrast to pre-existing handwashing stations using a bucket with a tap, Gravit'eau can save time and water resources by reducing the frequency of refilling the water tank from once a day to once a month. Consequently, more water can be saved for other purposes such as drinking or sanitation and the time efforts of the staff of the facility is reduced as well. Moreover, the station is built by local contractors using local materials, which enhances durability, facilitates maintenance and offers an opportunity to adapt the design to the needs of the facility and the context (like the size of the doors in facility, inside or outside, etc.). So far, the station has been tested in a laboratory at FHNW, in a German Music Festival, in mobile health clinics in Palestine, in child-friendly spaces and schools in Nigeria, and in health clinics in Mali. However, these tests did not involve long-term data collection. In order to scale up the use of Gravit'eau, the station needs to be tested in the field for at least nine months to take into account daily use, seasonal water shortages, local adaptation, and climate conditions.

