4 STUDY DESIGN

The overall project will follow an multi-center cluster-randomized controlled trial (cRCT) design (Figure 3). Prior to this study, the Facility and Evaluation Tool for WASH in Institutions (FACET)

has been used to assess the WASH infrastructure of the PHCFs in the study regions. From these PHCFs a subsample was identified which fulfils certain inclusion criteria (for the inclusion criteria see chapter 5.2 Inclusion criteria).

This subsample was handed over to the local Tdh collaborators who carefully assessed the security situation around the facilities. The Tdh collaborators then chose 24 facilities which are most probable to still be accessible for data collection within the next year. These 24 PHCFs will then be distributed into two arms (intervention vs. control) with stratified randomization using computer-generated randomization code provided by an statistician not involved in any field activities. The intervention arm will receive the full intervention package (handwashing station, behavioural change intervention, capacity development, management support, chlorination training and WASH FIT). The control arm will receive nothing for the duration of the intervention (9 months). Afterwards they will receive the same intervention package with potential improvements identified in the former intervention group.

In the chosen PHCFs all HCWs present at the day of data collection who fulfil the inclusion criteria will be asked to participate in the study. We aim to have as many of the HCWs in all of the Modules 1 and 3 as possible. For Module 2, only a maximum of 10 HCWs per facility will be observed.

[figure not shown]

Figure 3: Consort flow diagram of the PHCF selection for the h4h cRCT in Mali

The methods to achieve the different objectives of this project are summarized in Table 2. These modules will include qualitative and quantitative data approaches in order to enable a triangulation of the overall project results. The following modules will be used in the cRCT and the overall project: (i) Module 1: Combined RANAS and KAP survey, (ii) Module 2: Structured handwashing observations, (iii) Module 3: Microbiological analysis of hand rinse samples, (iv) Module 4: Diary approach for pre-defined health outcomes, (v) Module 5: Focus Group Discussions (FGDs) and (vi) Module 6: Key informant interviews (KIIs).

Table 2: Overview of different project modules and analysis by objective

Module	Objective	Analysis

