6.3.1 Datasets to be analysed, analysis populations

For the primary analysis we will use the available case population of HCWs which will be analysed according to the intention-to-treat principles.

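### Section 4.6 lets single sites be discontinued for rejection or technical failure of the package, reasons confined to the intervention arm, and nothing keeps those sites in the available-case primary comparison

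*Combined protocol and SAP*

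**What the plan says.** Section 4.6 opens the list of stopping reasons with "The overall h4h project or specific project sites can be discontinued due to several reasons by the project leader, such as". The list is open, has no thresholds and leaves the decision to the project leader. Three entries matter here:

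- "Ethical concerns (e.g. non-acceptance of proposed technical solutions"
- "Damage and vandalism of infrastructure, technical failure of interventions"
- "Alternative interventions and projects at the same facilities not coordinated with us"

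Section 4 describes the comparator: "The control arm will receive nothing for the duration of the intervention (9 months". For the primary analysis, section 6.3.1 says "we will use the available case population of HCWs which will be analysed according to the intention-to-treat principles". Section 6.4 rules out imputation. Section 6.3.1.2 offers covariate adjustment only, and no sensitivity analysis deals with lost facilities.

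Two other sections bear on the point. Section 4.3 provides a stopgap and repair when tests show a problem with a station. It also stops the study in a facility whose negative health outcomes are high and judged unusual. Section 5.4.1 lists reasons for discontinuing individual participants; rejection, technical failure, damage and parallel projects are not among them.

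**The concern.** Rejection and technical failure are results of the package. Section 2.3.1 says of the handwashing station that "the station needs to be tested in the field for at least nine months to take into account daily use, seasonal water shortages", so how it holds up in use is part of what the trial is meant to learn. If a site can be closed because the package failed there, and closure also ends measurement, the intervention arm is left with the sites where the package survived. The control arm has no matching exit, because it has no package to reject or to break.

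The analysis would still be called intention-to-treat, but it would estimate the effect among facilities that accepted and kept the package. That is a more favourable quantity than the one needed for a decision on scale-up, and outcomes never collected cannot be recovered at analysis. Section 4.3 states that participants, data collectors and the statistician are not blinded, and nothing says that a site decision is taken without knowledge of arm.

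**Working it through.** **Which reasons are tied to an arm.** Rejection of the technical solution and technical failure of the intervention need a package on site, so during the comparison they belong to the intervention arm. Damage or vandalism of infrastructure is not limited to study equipment and could occur at a control facility. An uncoordinated outside project could occur in either arm.

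**What is lost, and when.** Section 4.3 places the outcome rounds at two and nine months after the intervention. If closure ends measurement, a site closed before the two-month round contributes nothing after baseline. A site closed later keeps its two-month data and loses endline. Section 6.3 tests the arms at follow-up without naming the round. The synopsis uses that word for the middle round, as distinct from endline.

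**Inputs for an illustration.** The planning rates are 30% control and 45% intervention, a 15-point difference (6.2). The number of intervention sites K is 12 (4.4). It is 24 if the 48 facilities in the synopsis are split equally and both countries are pooled. The number of failed sites k and the share f of the effect that a failed site keeps are assumptions. Facilities are weighted equally and the effect is taken as a difference in proportions, whereas the planned model is a mixed logistic regression. The plan gives no figure of its own on this point to reproduce; the 81% power in 6.2 is not used.

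**Formulas.** With all facilities analysed, the difference is 15 × [1 − (1 − f) × k/K]. With the failed sites dropped, it stays at 15. The overstatement is 1/[1 − (1 − f) × k/K] − 1.

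| k | K = 12, f = 0 | K = 24, f = 0 | K = 12, f = 0.5 (failed sites at 37.5%) |
|---|---|---|---|
| 1 | 13.75 points, 9% | 14.375 points, 4% | 14.375 points, 4% |
| 2 | 12.5 points, 20% | 13.75 points, 9% | 13.75 points, 9% |
| 3 | 11.25 points, 33% | 13.125 points, 14% | 13.125 points, 14% |
| 4 | 10 points, 50% | 12.5 points, 20% | 12.5 points, 20% |

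Each cell gives the difference with all facilities analysed, then the overstatement from dropping the failures. For example, with k = 2, K = 12, f = 0: 15 × 10/12 = 12.5, and 15/12.5 = 1.20.

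**If the package does nothing.** A simulation with 12 facilities per arm, mean rate 30%, intracluster correlation 0.15, 30 opportunities per facility, a facility-level t-test and 8,000 runs per case removed low-rate facilities from the intervention arm only. Dropping the lowest 1, 2 or 3 gave a difference of about +2.2, +4.0 or +6.4 points and a type I error of 6.6%, 9.1% or 13.8%. Dropping 1, 2 or 3 at random from the lower half gave about +1.2, +2.7 or +4.4 points and 4.8%, 6.0% or 7.8%. This assumes that closure falls on facilities with low handwashing rates.

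**Reserve.** Section 6.2 needs 10 facilities per arm and enrols 24 in total, or 12 per arm. Two closures in one arm use up that arm's allowance for loss.

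**The case against.** The strongest reply is that the plan is silent here rather than wrong. Section 4.6 says only that sites may be discontinued and does not say whether that ends delivery, measurement or both. Section 4.3 sets out repair for a faulty station. Under 5.4.1, health workers at a site with a failed station would seem to remain participants. The analysis is declared intention-to-treat.

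Much of this stands, and it makes the loss less likely. It does not close the route. The repair provision follows integrity and water-quality tests and does not address rejection. Section 5.4.1 covers individuals and obliges nobody to visit a discontinued site. An intention-to-treat label cannot restore data that were not collected.

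Four stronger readings are tempting, and the documents do not support them:

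- A reader might infer that failures will drop out. This is an open possibility under a discretionary rule, not a stated consequence.
- A reader might take every listed reason as peculiar to the intervention arm. Damage and outside projects are not.
- A reader might suppose that outside projects occur more often at control facilities and so also favour the package. Nothing in the documents says so, and losing an intervention facility helped by such a project would push the other way.
- A reader might take 50% as an estimate. It needs four failures among 12 sites, all exactly at control level. The package also contains behaviour change, training and management support, so partial benefit is plausible.

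It can also be said that 45% is planned for the whole intervention arm, not for surviving sites. With f = 0 this leaves the ratio unchanged: if the arm averages 45% including two failures of 12 at 30%, dropping them gives 15 × 12/10 = 18 points against 15, again 20%.

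**Conclusion.** The concern holds as a gap that can bias the primary comparison. Two of the listed reasons can close sites in the intervention arm only, no text continues measurement there, and an available-case analysis without imputation would leave the missing facilities out. The bias from those two reasons would favour the package; for damage and outside projects the direction is unknown. If the two-month round is primary, only earlier closures affect the primary result, and later ones affect endline.

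The size cannot be established from the documents, because no failure count is given. The figures of 9% to 50% with 12 sites and 4% to 20% with 24 are illustrations for one to four failures at control level, and they shrink with partial benefit. The remedy is a cheap improvement in wording, worth making before any site is closed.

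**What to change.** Reword 4.6 so that rejection, damage, technical failure or a parallel project may end delivery of the package at a site but does not by itself end data collection. The remaining planned rounds of Modules 1 to 4 continue there where access and consent allow, and the facility is analysed in its randomised arm.

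Leave the other grounds for stopping as they stand: lost access, insecurity, withdrawn consent, other ethical concerns and the health-outcome stop in 4.3. A closed list of permitted stopping reasons would conflict with the last two.

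Reconcile 4.3, 4.6 and 5.4.1, so that it is clear when repair applies, when a site is discontinued, and what that means for its health workers as participants. Report package failures, parallel projects and discontinued sites by arm.

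The cost is a protocol amendment and no visits beyond those planned, though some will be made to sites where delivery has ended. The estimated effect may come out smaller.

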4.7 End of project

The biological material from the microbiological analysis will be destroyed upon completion of data analysis. Health-related data will be stored in an anonymized form for a minimum of 10 years at a password protected server of Swiss TPH. Photos, videos and recordings from the project will be stored on a password protected server of Swiss TPH, Terre des hommes or FHNW. If photos or videos contain pictures of people, they will be asked for their oral consent.

5 SELECTION OF STUDY PARTICIPANTS

5.1 Recruitment

Recruitment will differ according to the study modules. Participants will always be recruited within the clusters (HCFs). For the surveys (Module 1) and the microbial testing (Module 3), all HCWs in the intervention facilities will be targeted. For the handwashing observations (Module 2), a maximum of ten HCWs will be followed. If a PHCF has more than ten HCWs, they will be selected at random by drawing blindly their names from a closed bag. The patients who will be in contact with the HCWs during the observation period will all be asked to participate and to allow the observer to watch the interaction with an oral informed consent.

For the FGDs (Module 6), HCWs from the intervention arm of the h4h study will be invited to participate. If more than 3-4 HCWs are present at the day of the FGD, they will be selected randomly and asked for their consent to participate. In addition, the potential of inviting patients or their care takers will be explored in order to assess if the h4h intervention brings noticeable changes and improvements on the level of quality of care. Structures of hierarchy and gender in the health care facilities will be identified with the local partners to avoid mixing strongly differing hierarchies in mini groups of 3-4 participants. The group size of HCWs will be kept small as the participants should all have high expertise in hand hygiene in the intervention group (46). Depending on the hierarchical levels and if patients will be invited for discussion, one to four FGDs will take place per facility. If the FGDs are only done with HCWs, 6-10 FGDs per country will take

place or until saturation¹ is reached. In case interviews are held within the HCFs instead of FGDs, we expect to have 10-20 interviews or until saturation is reached.

For the KIIs (Module 7), local partners will be consulted on who they see as a suitable stakeholder for an interview. The sampling procedure will therefore be a purposeful sampling. Interviewees will be contacted by the local partners. Interviews will be held until saturation is reached.

5.2 Inclusion criteria

Study participants will be HCWs of the PHCFs which were chosen to be included in this study. PHCFs were chosen based on accessibility for the study teams, not having a water source directly connected to the building of the facility, having a maternity ward, having at least five employees and being impacted by conflict. All of the HCWs who are present in the PHCFs of the day of data collection will be invited to participate in the project for Modules 1 and 3.

Inclusion criteria Modules 1-3: HCWs must fulfil all the inclusion criteria:

- Minimum age of 18 years
- HCWs, men and women, who are in direct (body) contact with the patients

During the handwashing observations, health workers will consult with patients. In order to protect patients, they must meet these inclusion criteria for an observer to be allowed into the consultation room with them:

- Minimum age of 18 years or be accompanied by a legal guardian 18 years or older.
- Going to the SSE for a physical examination, injections/vaccinations or blood test.
- Oral consent to enter the room with them

Inclusion criteria Module 4: As the data will be collected on the health care facility level, all facilities in the project will be included.

Inclusion criteria Module 5:

- HCWs of the intervention facilities
- Minimum age of 18 years

Inclusion criteria Module 6:

- The participant needs to be:
 - a) a stakeholder within the community, state, region or country of the intervention who's position is related in any way to WASH in HCFs
 - b) working in one of the intervention PHCFs. They do not need to be HCWs, they can also be hygiene technicians or in a leading position of the facilities.
- Minimum age of 18 years

5.3 Exclusion criteria

Exclusion criteria Modules 1-3: HCW participants must not fulfil any of the following exclusion criteria:

- HCWs, whose primary occupation is not in the PHCF of the h4h project
- Suffering from any skin conditions not allowing the HCW to use soap or alcoholic hand rub
- Refusals to participate

Exclusion criteria Module 5: Refusals to participate.

¹ Saturation is reached when answers of participants start repeating and no new information can be gained through additional FGDs.

Exclusion criteria Module 6: Refusals to participate

5.4 Criteria for discontinuation of study

5.4.1 Discontinuation of individual participants

A participant can be discontinued from the study for the following reasons:

1. Withdrawal of informed consent
2. Changing work situation
3. Long-lasting absence of at least 6 months
4. Death
5. Inaccessibility of the HCF due to a high risk security situation

6 STATISTICS

6.1 Hypothesis

6.1.1 Primary hypothesis

The primary hypothesis stems from the research question: Does the h4h handwashing intervention package increase the hand hygiene of HCWs in PHCFs in Mali and Burkina Faso?

$H_{1.1}$ = The comprehensive h4h handwashing intervention increases hand hygiene in primary HCWs in Mali and Burkina Faso.

$H_{0.1}$ = The comprehensive h4h handwashing intervention will have no effect on hand hygiene of primary HCWs in Mali and Burkina Faso.

6.1.2 Secondary hypotheses

Depending on the secondary objective, different secondary hypotheses were formed:

$H_{1.1}$ = Hygiene-related RANAS variables will differ between participants based on their demographic indicators, previous training, and the water structures available in the health care facilities.

$H_{0.1}$ = Hygiene-related RANAS variables will not differ between participants based on their demographic indicators, previous training, and the water structures available in the health care facilities.

$H_{1.2}$ = Hygiene-related RANAS variables of health care providers in the intervention facilities will be significantly better compared to the health care providers in the control facilities.

$H_{0.2}$ = Hygiene-related RANAS variables of health care providers will be the same in health care providers of intervention and control facilities.

$H_{1.e}$ = Hygiene-related health outcomes will be significantly less frequent in intervention health care facilities compared to control health care facilities.

$H_{0.e}$ = Hygiene-related health outcomes will be the same in intervention health care facilities and control health care facilities.

